11.4.5.1.2 Progression-free Survival

PFS is defined as the time from the date of C1D1 to the date of the first documented progression or death due to any cause. PFS will be assessed via local review according to RECIST 1.1

(Eisenhauer et al., 2009). PFS will be censored in accordance with Table C1 in Appendix C in the FDA Guidance for Industry: Clinical Trial Endpoints for the Approval of Non-small Cell Lung Cancer Drugs and Biologics (FDA 2015).

Progression-free survival will be derived for all patients and presented graphically as well as summarized using survival analysis methods.

The quartile estimates of PFS from the Kaplan Meier product limit algorithm will be presented. The 2-sided 95% confidence interval will be presented as well. The number of events may be small, and thereby limit use of the Kaplan Meier method to provide reliable information. In this case, descriptive statistics (e.g., n, mean, standard deviation, median, minimum and maximum) for PFS will be presented.

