## 15.6 Progression free survival (PFS)

PFS is defined as the time from the date of C1D1 to the date of the first documented progression or death due to any cause. PFS will be assessed via local review according to RECIST  $1.1^2$ .

PFS will be censored in accordance with Table A in Appendix 3 in the FDA Guidance for Industry "Clinical Trial Endpoints for the Approval of Cancer Drugs and Biologics (2007)". In summary, PFS will be censored if no event (progression or death) is observed before the first of (i) the analysis cut-off date, and (ii) the date when a new anti-cancer therapy is started. The censoring date will be the date of the last adequate tumor assessment prior to cut-off/start of new anti-cancer therapy.

Subjects continuing without disease progression or death will be censored and the censoring date will be the date of the last adequate tumor assessment prior to data cut-off/start of new anti-cancer therapy. If there are no post-baseline scans available, then it will be censored at the date of the first IMP.

In case an event occurs after more than 2 missed scans, the censoring is done at last adequate assessment date before the missed scans. The definition of '2 missed scans' is equals to 98 days, the equivalent of 2 \* (6 weeks + 1 week of windowing).

If last scan date before the PD or death date is less or equal to 350 days (50 weeks) after start of IMP and the PD or death date is greater than 98 days (6+1 weeks \*2) after this last scan date, then it will be censored at last scan date.

If last scan date before PD or death date is greater than 350 days (50 weeks) and less or equal to 441 days (50+13 weeks) after start of IMP and the PD or death date is greater than 140 days (50+13 weeks) after this last scan date, then it will be censored at last scan date.

If last scan date before the PD or death date is greater than 441 days (7+13 weeks) after the start of IMP and PD or death date is greater than 182 (12+1 week \*2) days after this last scan date, then it will be censored at last scan date.

Progression-free survival will be derived and listed for all subjects as well as summarized using survival analysis methods:

- Kaplan-Meier curves
- Kaplan-Meier estimate of the median time, the first and third quartiles, along with approximate 95% confidence interval of the median (the default conftype=loglog in SAS PROC LIFETEST will be used).

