The number of events may be small, and thereby limit use of the Kaplan Meier method to provide reliable information. In this case, descriptive statistics (e.g., n, mean, standard deviation, median, minimum, and maximum) for PFS will be presented.

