## 15.7 Duration of response (DoR)

Page 21 of 44

TPL N°: eTPL SA-02-01 Of SOP SA-02.08 TPL Effective Date: 31 Mar 2016

Duration of response (DOR) only applies to the subset of subjects in the FAS whose confirmed best overall response is CR or PR. The start date is the date of first documented response of CR or PR (i.e., the start date of response, not the date when response was confirmed), and the end date is defined as the date of the first documented disease progression.

Version: 2.0

Page 22 of 44

DoR will be analysed using the censoring rules based on the FDA guideline, see section 15.3.

DOR (months) will be listed for all subjects in the FAS with best overall response of CR or PR, and presented graphically as well as summarized using survival analysis methods:

- Kaplan-Meier curves
- Kaplan-Meier estimate of the median time, the first and third quartiles, along with approximate 95% confidence interval of the median (the default conftype=loglog in SAS PROC LIFETEST will be used), and the range.

The number of events may be small and limit use of the Kaplan-Meier method to provide reliable information. In this case, descriptive statistics (n, mean, SD, median, minimum, and maximum) will be presented.

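### The few-events fallback for PFS and DoR (SAP 15.6, 15.7) gives plain summary statistics with no trigger and no rule for censored times, and understates both endpoints where censoring is appreciable

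*SAP*

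**What the plan says.** SAP 15.6 defines PFS with censoring. On subjects without an event it says: "Subjects continuing without disease progression or death will be censored and the censoring date will be the date of the last adequate tumor assessment". On subjects never scanned after baseline: "If there are no post-baseline scans available, then it will be censored at the date of the first IMP". It continues: "Progression-free survival will be derived and listed for all subjects as well as summarized using survival analysis methods". Kaplan-Meier curves, median and quartiles follow.

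The fallback comes next: "The number of events may be small, and thereby limit use of the Kaplan Meier method to provide reliable information", and then "In this case, descriptive statistics (e.g., n, mean, standard deviation, median, minimum, and maximum) for PFS will be presented".

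SAP 15.7 has the same construction for DoR: "In this case, descriptive statistics (n, mean, SD, median, minimum, and maximum) will be presented". DoR is also a censored variable: "DoR will be analysed using the censoring rules based on the FDA guideline, see section 15.3". Section 15.3 is the best overall response section and holds no censoring rules, so 15.6 is presumably meant. Protocol 11.4.5.1.4 censors DoR at the last adequate tumor assessment.

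The fallback comes from protocol 11.4.5.1.2, which warns that few events may "limit use of the Kaplan Meier method to provide reliable information". The protocol synopsis applies it to PFS, OS and DoR together.

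Two parts of the SAP go the other way. Section 4 prescribes Kaplan-Meier summaries for time-to-event parameters with no exception for few events. Section 15.8 (OS) has no fallback.

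**The concern.** A plain mean or median needs one complete number per subject. A censored subject supplies only a lower bound. If all derived times are used, that lower bound is counted as though progression happened then. If only event times are used, the subjects still event-free are dropped, and those with longer times tend to be among them. Both routes pull the summary down when censoring is material, and the SAP does not say which applies.

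The rule for subjects with no post-baseline scan adds to this. Each has a time near zero. Such a subject leaves the Kaplan-Meier risk set at once and has almost no influence on the estimate, but carries full weight in a plain mean.

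At stake is the PFS or DoR summary shown by dose level. A reader could take a figure that partly reflects length of follow-up for an estimate of the endpoint.

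**Working it through.** The documents give no expected PFS or DoR, so there is no planned figure to reproduce. The inputs below are assumptions, except the total of 48 subjects (SAP 3.3).

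**Hand example.** Six times in months: 1.4, 1.4, 2.8, 2.8, 4.1, 5.5. One of the 1.4s and one of the 2.8s are events; the rest are censored.
- Plain mean: 18.0/6 = 3.0. Plain median: 2.8. Mean of event times only: (1.4 + 2.8)/2 = 2.1.
- Kaplan-Meier: 5/6 after 1.4, then 5/6 × 3/4 = 0.625 after 2.8. It never falls to 0.5, so the median is not reached.
- If all six were events, the plain and Kaplan-Meier medians would both be 2.8.

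**General size.** Assume exponential event times with true median 4.0 months, so mean 4.0/ln 2 = 5.77, and independent exponential censoring with a fraction c censored. The recorded time is then exponential with its mean and median both multiplied by (1 − c):
- Plain median = 4.0 × (1 − c): 3.6, 2.8, 2.0 and 1.2 for c = 10%, 30%, 50% and 70%.
- Plain mean = 5.77 × (1 − c): 5.19, 4.04, 2.89 and 1.73.

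In this model the recorded time is independent of whether it ends in an event, so event times only give the same values. Simulation with n = 48 and 3,000 replicates agrees (plain medians averaged over replicates; Kaplan-Meier as the median over replicates, with not reached counted as large):

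| Censored | Plain median, all times | Plain median, events only | Kaplan-Meier median |
|---|---|---|---|
| 10% | 3.64 | 3.65 | 3.96 |
| 30% | 2.84 | 2.87 | 4.00 |
| 50% | 2.04 | 2.05 | 4.03 |
| 70% | 1.22 | 1.26 | 4.09 |

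Uniform censoring gives the same direction: at 54% censored, 2.19 on all times and 1.73 on events only.

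**Small groups.** With n = 6, and medians over replicates for both, plain against Kaplan-Meier is 3.73 vs 3.27 at 10% censored, 3.27 vs 3.32 at 20%, 2.85 vs 3.52 at 30% and 2.04 vs 3.74 at 50%. Up to about 20% the plain median is not materially below Kaplan-Meier. Both are noisy at this size and depend on how a median is picked from an even number of times.

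**Censoring at first dose.** If 6 of 48 subjects had no post-baseline scan, their near-zero times would multiply the plain mean by about 42/48 = 0.875, a cut of 12.5%.

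**The case against.** The strongest reply is that few events need not mean heavy censoring. The default cohort is 3 patients, the first cohort was a single patient (protocol 4.3), and 48 subjects are spread mainly over six biweekly dose levels (SAP 3.3, 4.5). A dose level of three subjects who all progressed has few events and an unbiased plain median. This stands. A reader might infer that the fallback operates exactly where its bias is greatest, but the trigger is the number of events and the bias comes from the share censored.

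A reader might also infer that the SAP drops Kaplan-Meier, or instructs that censored times be counted as events. Neither is written. Replacement is the natural reading of a fallback for when Kaplan-Meier is unreliable, but presenting the statistics in addition is not excluded. On censored times the SAP is silent. This does not rescue the fallback: both ways of computing the statistics understate under appreciable censoring, and an addition would put a biased median beside a valid one.

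Heavy censoring may also be unlikely. The final analysis is at trial completion (SAP 4.2), 27 subjects had been exposed by 20 August 2019 (protocol 2.3), and SAP version 2.0 is dated February 2022. This makes 70% or more censored hard to assume. Some censoring remains likely, because new anti-cancer therapy, long gaps in scanning and absent post-baseline scans all censor PFS, but the documents do not allow its extent to be estimated.

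Finally, no decision rests on these summaries. PFS and DoR are secondary and untested, the primary endpoint is dose-limiting toxicity, the MTD has been found and the expansion was not initiated. This limits the severity.

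**Conclusion.** The fallback is unsound as written for any group with appreciable censoring, and the SAP gives neither a trigger nor a censoring rule to contain it. Under the assumed exponential model with independent censoring and n = 48, the plain median falls short of a true 4.0 months by about 10% of its value at 10% censored, 30% at 30% and 50% at 50%. The sizes depend on that model and on a censoring fraction the documents do not give. The downward direction also held under uniform censoring. There is no understatement in a group where everyone has an event, and none that matters at n = 6 with 10 to 20% censored.

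A reader might go further and expect dose levels with shorter follow-up to look worse. That would follow if follow-up differed between dose levels, but the documents do not show that it does. Severity is minor to moderate.

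**What to change.** Delete the fallback sentence in SAP 15.6 and 15.7. State that Kaplan-Meier is always reported for PFS and DoR, as SAP section 4 already requires, with the numbers of events and censored subjects and 'not reached' where it applies. Where events are too few for a useful estimate, rely on the planned individual listing (Listing 16.02.02.03) and specify a censoring flag in it. Record the departure from protocol 11.4.5.1.2 and the synopsis in SAP section 5. Median follow-up by reverse Kaplan-Meier is optional.

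The cost is SAP wording, one entry in section 5 and minor programming, since the Kaplan-Meier outputs and the listing are already planned. The downside is that some dose levels will show no median or no interval. In the illustration with n = 6, the Kaplan-Meier median was not reached in 17% of replicates at 50% censored and 41% at 70%. That is a fair report of what such data can support.

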## 15.7 Duration of response (DoR)

Page 21 of 44

TPL N°: eTPL SA-02-01 Of SOP SA-02.08 TPL Effective Date: 31 Mar 2016

Duration of response (DOR) only applies to the subset of subjects in the FAS whose confirmed best overall response is CR or PR. The start date is the date of first documented response of CR or PR (i.e., the start date of response, not the date when response was confirmed), and the end date is defined as the date of the first documented disease progression.

Version: 2.0

Page 22 of 44

DoR will be analysed using the censoring rules based on the FDA guideline, see section 15.3.

DOR (months) will be listed for all subjects in the FAS with best overall response of CR or PR, and presented graphically as well as summarized using survival analysis methods:

- Kaplan-Meier curves
- Kaplan-Meier estimate of the median time, the first and third quartiles, along with approximate 95% confidence interval of the median (the default conftype=loglog in SAS PROC LIFETEST will be used), and the range.

The number of events may be small and limit use of the Kaplan-Meier method to provide reliable information. In this case, descriptive statistics (n, mean, SD, median, minimum, and maximum) will be presented.

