8.2 Withdrawal from the Trial

Patients will be withdrawn from the trial (dose escalation or expansion parts), including safety follow-up evaluations and follow-up contact, for the following reasons:

- A patient may withdraw from the trial at any time at his or her own request
- At the discretion of the investigator for safety, behavioral, compliance, or administrative reasons
- Lost to Follow-Up (see Section 8.4)
- Patient died
- Trial closure
- Initiation of other anti-cancer treatment (the dose-escalation part only)

If the patient withdraws consent for disclosure of future information, the sponsor may retain and continue to use any data collected before such a withdrawal of consent.

If a patient withdraws from the trial, he or she may request destruction of any samples taken and not tested, and the investigator must document this in the site trial records.

The sponsor will make any effort to ensure patients are followed up for completion of safety assessment in the trial. See Table 1-1 and Table 1-6 for data to be collected at the time of trial discontinuation and follow-up and for any further evaluations that need to be completed.

When a patient withdraws before completing the trial, the reason for withdrawal is to be documented in the eCRF and in the source document. Trial drug assigned to the withdrawn patient may not be assigned to another patient.

Patients who withdraw will not necessarily be replaced.

Withdrawal From the Use of Samples in Future Research

The patient may withdraw consent for use of samples for research (refer to Section 13.2.5). In this case, samples will be destroyed after they are no longer needed for the clinical trial. Details of the sample retention for research are presented in the ICF.

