11.4.5.1 Secondary Efficacy Endpoints

11.4.5.1.1 Definition of Response

RECIST criteria (v1.1) will be used to define response. Based on the definition of response (Table 11-2) and the combined evaluation (see Table 1 in Eisenhauer et al., 2009), each patient will be assigned 1 of the following categories at each CT scan visit and as Best Overall Response (BOR):

1) CR

2) PR

3) SD

4) PD or

5) Not Evaluable

BOR is the best response recorded from the start of the treatment until disease progression/recurrence (the smallest measurements recorded since the treatment started will be used as the reference for PD).

	Category	Criteria
Based on	Complete	Disappearance of all target lesions. Any pathological lymph nodes must
target lesions	Response (CR)	have reduction in short axis to < 10 mm.
	Partial Response	\geq 30% decrease in the sum of the LD of target lesions, taking as reference
	(PR)	the baseline sum of LDs.
	Stable Disease	Neither sufficient shrinkage to qualify for PR nor sufficient increase to
	(SD)	qualify for PD, taking as reference the smallest sum of LDs while in trial.
	Progressive	\geq 20% (and \geq 5 mm) increase in the sum of the LDs of target lesions, taking
	Disease (PD)	as reference the smallest sum of the target LDs recorded while in trial or the
		appearance of 1 or more new lesions.
	NE	Not evaluable
Based on non-	CR	Disappearance of all non-target lesions and normalization of tumor marker
target lesions		level. All lymph nodes must be non-pathological in size (< 10 mm short
		axis).
	SD	Persistence of 1 or more non-target lesion(s) or/and maintenance of tumor
		marker level above the normal limits.
	PD	Appearance of 1 or more new lesions and/or unequivocal progression of
		existing non-target lesions.
	NE	Not evaluable

 Table 11-2 Definition of Response (RECIST Criteria v1.1)

LD =Longest Diameter; SD for non-target lesions defined as "Non-CR/Non-PD" by Eisenhauer et al., 2009.

Patients with a global deterioration of health status requiring discontinuation of treatment without objective evidence of PD at that time should be classified as having "symptomatic deterioration". Every effort should be made to document the objective progression even after discontinuation of treatment.

Confirmation

SD: follow-up measurements occurring at least 6 weeks (\pm 7 days) after first treatment must have met the SD criteria at least once.

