11.4.5.1.4 Duration of Response

Duration of response (DoR) only applies to patients whose best overall response is complete response (CR) or partial response (PR) and is defined as the number of days from the first documentation of objective tumor response (CR or PR) to the date of first PD or death due to underlying cancer. Subjects continuing without progression or death due to underlying cancer will be censored at the date of their last adequate tumor assessment.

DoR will be summarized in the same way as PFS.

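### SAP 15.7, read literally, ends duration of response at documented progression only; the protocol also counts death from the underlying cancer, the difference is undeclared, and the censoring pointer leads to the wrong section

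*SAP*

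**What the plan says.** Protocol 11.4.5.1.4 runs DoR from the first documented response "to the date of first PD or death due to underlying cancer". Its only censoring rule is: "Subjects continuing without progression or death due to underlying cancer will be censored at the date of their last adequate tumor assessment".

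SAP 15.7 starts DoR at the same point, for subjects with a confirmed CR or PR, but "the end date is defined as the date of the first documented disease progression". Death is not mentioned. On censoring it says: "DoR will be analysed using the censoring rules based on the FDA guideline, see section 15.3".

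SAP 15.3 is the section on best overall response. It gives response categories, confirmation sequences and a 35-day rule for stable disease. It mentions new anti-cancer therapy only as the end of the window for best response.

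The FDA-based censoring rules are in SAP 15.6, on PFS, where the event is progression or death from any cause: "Subjects continuing without disease progression or death will be censored". One of its censoring triggers is "ii) the date when a new anti-cancer therapy is started". Another is a long gap between the last scan and the event.

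SAP section 5 lists three changes from the protocol: the dose-determining set, the PK analysis set and the unused expansion part. DoR is not among them, and the SAP version history does not mention it.

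**The concern.** A programmer who follows the SAP 15.7 sentence as written gives no DoR event to a confirmed responder who dies of the cancer before progression is documented. The protocol gives that subject an event on the date of death. The summary would then depart from the protocol definition, and nothing in the SAP tells the reader so. In a Kaplan-Meier analysis the usual direction flatters the drug, because an event becomes a censored time.

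The protocol foresees a route to this case. Section 11.4.5.1.1 describes "Patients with a global deterioration of health status requiring discontinuation of treatment without objective evidence of PD at that time". The same paragraph asks sites to keep trying to document progression after treatment stops, which makes the case less likely but does not remove it.

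**Working it through.** The documents state no DoR figure, so there is nothing to reproduce. The check is a comparison of texts, followed by an illustration of size.

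**Definitions side by side**

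| Source | Event | Censoring |
|---|---|---|
| Protocol 11.4.5.1.4 | PD or death from the underlying cancer | Last adequate tumor assessment if neither has occurred |
| SAP 15.7, literally | Documented PD only | Refers to 15.3, which has no censoring rules |
| SAP 15.7 with the pointer read as 15.6 | 15.7 says PD only; the 15.6 rules assume PD or any death | Last adequate assessment before new therapy; also when PD or death comes too long after the last scan |

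Correcting the pointer alone does not settle the matter. Three events remain possible: PD, PD or cancer death, and PD or any death. The phrase about the FDA guideline does not help either, because protocol 11.4.5.1.2 cites the 2015 guidance, SAP 15.6 cites the 2007 guidance, and the SAP reference list gives 2015.

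**Who is affected**

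Under the 15.6 rules, an event after new therapy or after too long a gap is censored under every reading. The gap limits are 98, 140 or 182 days, depending on when the last scan took place. This leaves a cancer death without documented PD, before new therapy and within the gap limit. Protocol 8.2 narrows the case further, since one ground for withdrawal from the trial is "Initiation of other anti-cancer treatment (the dose-escalation part only"), so deaths after new therapy would often not be observed in any case.

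**Illustration of size (assumptions, not trial data)**

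- *Responders.* SAP 3.3 gives 48 subjects. Applying the historical rates of protocol Table 11-6: 48 × 2% = 0.96 and 48 × 10% = 4.8, or about 1 to 5. SAP 4.5 puts the priming and intensified subjects in listings only. With the 1 + 3 subjects of SAP 3.3 removed, 44 × 2% = 0.88 and 44 × 10% = 4.4.
- *f*, the share of protocol DoR events that are such deaths: not in the documents. Assumed 5%, 10% and 20%.
- *Chance of at least one affected responder*, 1 − (1 − f)^n. For n = 1: 5%, 10%, 20%. For n = 5: 1 − 0.95^5 = 23%, 1 − 0.90^5 = 41%, 1 − 0.80^5 = 67%.
- *Simulation*, 20,000 trials, n = 5. Scans every 6 weeks to week 48, then every 12 weeks from week 60. Response starts at week 6. Time to PD or PD-free cancer death is exponential with an assumed median of 180 days. PD is dated at the next scan. The affected death is an event under the protocol and is censored at the last scan under literal 15.7. There is no other censoring. The median is the first time the curve is at or below 50%.

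| f | KM median longer or unreached | Unchanged | Shorter | Fall in fallback mean |
|---|---|---|---|---|
| 5% | 8% | 92% | 0% | 1.3 days |
| 10% | 16% | 84% | 0% | 2.7 days |
| 20% | 31% | 69% | 0% | 5.3 days |

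The fallback means come from a large sample: 287.1 to 285.8, 286.0 to 283.3, and 283.0 to 277.7 days.

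**Direction**

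On a common scan schedule, as simulated, no other counted event falls between the deceased subject's last scan and the death, so the curve can only stay the same or rise. If scan dates differ between responders, another progression can fall in that interval. With n at risk, its step factor is then (n − 2)/(n − 1) instead of (n − 1)/n, so the curve can be slightly lower until the date of death. This is a minor qualification. In the fallback, the affected time ends at the last scan instead of at death, so it can only be equal or shorter.

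**The case against.** *The literal reading is not the only one.* SAP 15.7 says FDA-based censoring applies, and within SAP section 15 only 15.6 sets out such rules. A programmer who follows them could count the death. The text fits an incomplete sentence and a stale cross-reference as well as it fits a changed endpoint. This stands: a reader might infer that the sponsor deliberately redefined DoR, and the documents do not show that. They show an ambiguity, which still has to be resolved.

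*Restoring the event does not bring DoR fully back to the protocol.* This also stands. Protocol 11.4.5.1.4 does not censor at new therapy or after missed scans. Its remark that DoR is summarized like PFS concerns presentation. The restriction to confirmed CR or PR in SAP 15.7 is a further difference: protocol 11.4.5.1.1 requires no formal confirmation of response, whereas 11.4.5.1.5 requires it expressly for time to response.

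*The size is weakly supported.* This stands as well. The values of f have no source. The response rates are historical rates for expansion cohorts that never opened, applied here to a mixed dose-escalation population reported by dose level. With 1 to 5 responders, SAP 15.7 itself foresees descriptive statistics, where the effect is nil or in the other direction. The 31% combines the highest f, the highest responder count and the Kaplan-Meier option.

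*An affected responder could be found.* SAP Listing 16.02.02.03 shows DoR and OS together, and SAP 17.4 lists the primary cause of death. This limits the harm but does not correct the summary in Table 14.02.02.03.

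**Conclusion.** The point holds as a definitional conflict. SAP 15.7, read literally, omits an event that protocol 11.4.5.1.4 counts, section 5 does not declare the difference, and the censoring pointer leads to a section without censoring rules. Reading the pointer as 15.6 replaces a gap with a contradiction.

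The consequence is limited. The affected case is narrow, its frequency is not given, and the effect is probably small. If no responder dies this way, the event definitions give the same result. The simulation is illustrative only and rests on assumed f, responder count and median. A reader might infer that reported DoR is inflated. The documents do not support that: they show no affected responder, and the descriptive fallback moves the other way if it moves at all. DoR is an untested secondary endpoint, and the MTD is unaffected. The correction should be made, but no main conclusion of the trial depends on it.

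**What to change.** 1. In SAP 15.7, define the end date as the earlier of first documented progression and death from the underlying cancer, with deaths from other causes censored at the last adequate tumor assessment.
2. Change the pointer from 15.3 to 15.6, and state that the 15.6 censoring rules apply to the DoR events so defined. Refer to 15.6 by number, since the two documents cite different FDA guidances.
3. In SAP section 5, list what still differs from protocol 11.4.5.1.4: censoring at new anti-cancer therapy, censoring after missed scans, and the restriction to confirmed CR or PR. If the sponsor prefers death from any cause, to match PFS, list that too.
4. When 15.6 is reused, correct its labels. The 140-day limit is labelled 50+13 weeks but is (6+1) + (12+1) = 20 weeks = 140 days. The 441-day limit is labelled 7+13 weeks in one place but is 50 + 13 = 63 weeks = 441 days.

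The cost is a few sentences in the SAP, one cross-reference and two label corrections. Cause of death is already collected and listed, so no new data are needed. No protocol amendment is needed to restore the protocol event.
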